This is a pre-/post-evaluation of a diabetes prevention clinical pathway that will be implemented over a 12-month period at the intervention clinic. Eligible patients include those on the prediabetes registry who are seen in the control and intervention clinics during the study period. Their first visit with the PCP will be considered V0 (initial data collection) and data will be collected retrospectively (12 months prior to V0) and prospectively at that visit and subsequent primary care visits (V1, V2, V3, etc.) during the 12-month intervention period (see Figure).

The diabetes prevention clinical pathway will focus on the following steps: 1) Screen/test-testing of eligible patients for prediabetes/diabetes, 2) Education- PCPs will be encouraged to take an online learning module and in-person group training on prediabetes management, and patients with prediabetes will receive a handout about prediabetes prior to their upcoming PCP visit, 3) Action- PCPs will use a shared decision-making guide and treatment algorithm to discuss options with patients at their visit, 4) Referral- patients may be referred to DPPs and/or medical nutrition therapy (MNT), and 5) Treat- patients will be scheduled for a follow-up visit within 3-9 months with their PCP or care team (NP) to continue addressing prediabetes.

Group 1 Intervention clinic patients

PCPs in the intervention clinic will be invited and encouraged to attend the 1-hour clinician training session at the beginning of the intervention. This is considered continuing medical education, and we may be able to provide continuing medical education credit for their attendance. The training session will include information on prediabetes treatment guidelines, use of EPIC clinical decision support tools and use of the patient handout to discuss treatment options. There will be interactive skills practice incorporated. This training session may occur on up to 2 occasions to capture all PCPs. We may also record the training session so that PCPs who could not attend can view it later asynchronously.

Patients with prediabetes (e.g., “active” on prediabetes registry) presenting for a routine visit in the intervention clinic will be identified using an EPIC workbench report run the week prior to their upcoming visit. These patients, presenting for in-person or video visits, will receive the handout as an attachment either via MyChart or via email sent from REDCap.

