Enrolled participants will be monitored throughout the study for untoward incidents (e.g., “Adverse Events”) occurring during the study. The Principal Investigator (and other designated individuals, if necessary) will conduct regular monitoring for safety concerns and provide general oversight for human subject safety requirements. Where necessary these occurrences will be evaluated for severity, attribution, and possible trends. All adverse events that are anticipated or described in the informed consent form will be logged appropriately and reported to the IRB on at least an annual basis (e.g., at continuing review).

Any Unanticipated Problems or unexpected “Serious Adverse Events” *related* to the study intervention or affecting the risk/benefit profile of the study, will be reported to the IRB promptly, and, in all cases, within 10 business days of discovery. Unplanned and non-emergent deviations from the IRB approved protocol will be logged and reported to the IRB annually at continuing review; all planned deviations will be submitted as a Change in Research to the IRB for approval and prior to implementation. All other event reporting requirements will be followed and all necessary parties will be notified of events/problems encountered in the study and/or changes in research, in accordance with all applicable regulations and guidelines.

Statistical Plan

Sample Size Determination and Power

We estimate that 1200 patients with prediabetes will be seen over the 12-month intervention period within each clinic (total sample of 2400 patients). Based on this sample, we estimate we will have 100% power to detect a change in rate of referral to DPPs from 0% to 25%. Additionally, we estimate that we will have 100% power to detect a change in documented prediabetes diagnosis from 10% (baseline rate estimated from Johns Hopkins data) to 34% (national estimate of the prevalence of prediabetes), follow-up lab testing completed from 50% (baseline rate estimated from Johns Hopkins data) to 60%, and referral to nutrition from 1% (baseline rate estimated from Johns Hopkins data) to 10%. In our analysis, we will assess the differences in trend of the outcomes in the baseline, intensive implementation, and sustainment periods.

Primary outcome variable

The primary outcome is whether patients with prediabetes are referred to a DPP and/or medical nutrition therapy and/or start metformin.

Secondary outcome variables

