The secondary outcomes are whether patients: 1) enroll in the DPP, 2) attend a medical nutrition therapy visit, 3) complete follow-up glycemic testing, 4) fill metformin, 5) achieve weight loss $\geq 5\%$ and 6) complete PCP/team follow-up visit.

Other process outcomes we will look at include whether MyChart messages with the prediabetes handout are read.

Statistical Methods

For the analysis, we will include patients with prediabetes (identified by prediabetes registry) who have completed at least once PCP visit during the first 6 months of the 12-month intervention period. We will compare the primary outcomes and other secondary outcomes between the intervention and control clinics.

We will conduct an interrupted time series analysis to evaluate the differences in trend of the outcomes in the baseline (V0-12m), intensive implementation (T0-T6m), and sustainment periods (T6m-T12m) at the patient level. We will compare these outcomes in the pre- and post-intervention periods using logistic regression models with generalized estimating equations to account for repeated observations within patients. We will use multivariate logistic regression models to determine predictors of these outcomes adjusting for race, age, and baseline HbA1c. We may adjust for clinic-level characteristics, such as patient safety culture using GLINT survey data from 2021 and 2022 if available. We will only request aggregate data from the clinic-level on safety culture.

Study Administration

Funding Source

Funding for this study is provided by the National Institute of Diabetes and Digestive Kidney Diseases under Award Number K23DK118205 (PI: [name]).

Subject Stipends and Payments

Patients who complete the survey will receive a \$10 gift card, either mailed to their home address or sent as an e-gift card based on patient preference. The last survey question will ask them to provide this information, which will not be linked to other responses. Clinicians who

complete the survey will get a \$25 e-gift card sent to the email address they provide. Again, their response to this question will not be linked to other responses.

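### The control clinic is named as comparator, but no clinic-by-period term links it to the pre/post data, and no contrast is designated as the pathway effect

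*Combined protocol and SAP*

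**What the plan says.** The comparator is clear. The Primary Hypothesis and Study Objectives both set the intervention clinic against a control clinic, and the Study Design overview describes a non-randomised study with one comparison group. Eligible patients come from both clinics, with data from the 12 months before their first visit (V0) and from the 12-month implementation period.

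Statistical Methods then lists:

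- A between-clinic comparison, with no period, model or effect measure: "We will compare the primary outcomes and other secondary outcomes between the intervention and control clinics".
- A time series over baseline, intensive implementation and sustainment, with clinic not mentioned: "We will conduct an interrupted time series analysis to evaluate the differences in trend of the outcomes".
- A pre/post model, again with clinic not mentioned: "We will compare these outcomes in the pre- and post-intervention periods using logistic regression models with generalized estimating equations".
- A predictors model "adjusting for race, age, and baseline HbA1c". Adjustment for clinic-level characteristics such as safety culture is optional.

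Elsewhere the emphasis is on periods. Study Procedures says: "This is a pre-/post-evaluation of a diabetes prevention clinical pathway that will be implemented over a 12-month period at the intervention clinic". The power section says: "we will assess the differences in trend of the outcomes in the baseline, intensive implementation, and sustainment periods". It states power for a change in a rate, without saying whether that is pre to post or between clinics. A primary outcome is named (the composite of DPP referral, nutrition referral or metformin start); a primary contrast is not.

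**The concern.** The listed contrasts answer different questions and can disagree.

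The pre/post contrast, and a time series without clinic terms, cannot separate the pathway from change that also occurs in the control clinic. The documents supply a candidate. The Introduction says a DPP referral order was not in place until recently. The order sits in an Epic smartset, and control-clinic physicians have the same Epic tools. DPP referral is a component of the primary outcome. Only intervention-clinic physicians are trained in these tools, so part of their use is a genuine pathway effect; a clinic-by-period term would keep that part and remove the shared part.

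The between-clinic contrast is protected from shared change but absorbs any difference present before launch. Baseline outcome rates are not among the named covariates.

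The Introduction plans system-wide implementation and testing if this pilot succeeds. At stake is a misread pilot result, when the data for a contrast net of both problems are already being collected.

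**Working it through.** **Inputs.** From the documents: 1200 patients per clinic; planned effects of DPP referral 0% to 25%, diagnosis 10% to 34%, lab testing 50% to 60% and nutrition referral 1% to 10%; earlier cohort rates of 1.0% nutrition referral and 5.4% metformin. Assumed: two-sided alpha 0.05 (none is stated); composite baseline 1.0% + 5.4% = 6.4% (no overlap, DPP 0%); T0 as clinic launch; the date and size of any shared change; any baseline clinic difference; within-patient pre/post correlation ρ; and 600 per clinic as a possible size after the first-6-month visit rule.

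**1. The plan's own power.** Two-sample test, 1200 against 1200, lab testing: Φ[(0.10 − 1.96 × √(0.55 × 0.45 × 2/1200)) / √((0.25 + 0.24)/1200)] = 99.9%. The other three effects exceed 99.9%. The stated 100% is sound for a simple two-group contrast.

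**2. Shared change, no pathway effect, pre/post contrast.** Suppose the composite doubles to 12.8% in both clinics, k months before T0, and the post period is wholly at 12.8%. With m months of the 12-month baseline after the step, the baseline rate is [6.4%(12 − m) + 12.8%m]/12. With windows anchored at T0, m = k. With baseline anchored to V0, as the plan has it, and V0 spread evenly over the first 6 months, m is the average of min(12, k + u) for u from 0 to 6.

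| k (months) | T0 anchor: baseline, OR | V0 anchor: baseline, OR |
|---|---|---|
| 0 | 6.4%, 2.15 | 8.0%, 1.69 |
| 3 | 8.0%, 1.69 | 9.6%, 1.38 |
| 6 | 9.6%, 1.38 | 11.2%, 1.16 |
| 9 | 11.2%, 1.16 | 12.4%, 1.04 |
| 12 | 12.8%, 1.00 | 12.8%, 1.00 |

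If the rate rises only by a quarter, to 8.0%, the ranges are 1.00 to 1.27 (T0) and 1.00 to 1.19 (V0).

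**3. Baseline clinic difference, no pathway effect, between-clinic contrast.** Control 6.4%; intervention-clinic odds 1.5 times higher, so 9.3%. SE of the log OR = √[1/(1200 × 0.064 × 0.936) + 1/(1200 × 0.093 × 0.907)] = 0.154; z = 0.405/0.154 = 2.63; probability of significance about 75%. In simulation the clinic-by-period interaction rejects in 5% of runs, as it should.

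**4. Power of the interaction (risk-difference scale).** For one clinic moving from a to b, the variance of its change is V(a,b) = [a(1−a) + b(1−b) − 2ρ√(a(1−a)b(1−b))]/n. The interaction SE is √[V(intervention) + V(control)], and power is Φ(d/SE − 1.96), where d is the intervention change minus the control change.

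Lab testing, flat control, n = 1200, ρ = 0: SE = √(0.99/1200) = 0.0287; 0.10/0.0287 = 3.48; power 93.6%. With the intervention clinic always reaching 60%:

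| n per clinic | Control rise | ρ = 0 | ρ = 0.3 | ρ = 0.5 |
|---|---|---|---|---|
| 1200 | 0 points | 93.6% | 98.6% | 99.8% |
| 1200 | 2 points | 79.6% | 91.5% | 97.6% |
| 1200 | 5 points | 41.4% | 54.9% | 69.3% |
| 600 | 0 points | 69.2% | 83.7% | 93.6% |

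With a flat control clinic, DPP referral, diagnosis and nutrition referral stay at about 100%, even at 600 per clinic (SEs 0.0177, 0.0287 and 0.0141 for differences of 0.25, 0.24 and 0.09, ρ = 0).

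**The case against.** The strongest reply is that a controlled analysis is already implied. The hypothesis, the objective and the first analysis sentence all make the control clinic the comparator. The time series and GEE sentences follow that comparison, and nothing confines them to one clinic. The optional adjustment for clinic-level characteristics makes sense only if both clinics are in a model. This stands as far as it goes: a controlled reading is possible. But it is not written down, the clinic-level adjustment is optional, and with two clinics such a covariate cannot be separated from clinic and cannot replace the interaction. Two analysts could follow the text faithfully and report different pathway effects.

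A reader might go further and infer that the plan ignores its control clinic, or has committed to a biased analysis. The documents do not support that: the comparator is named, and silence about clinic terms is not exclusion. Nor do they support a claim that the referral order inflates the result by a known amount. Its date is not given, and if it preceded the whole baseline window its contribution to the pre/post contrast is nil. The plan speaks of trend differences without defining the time-series parameters, so no bias is quantified for that analysis.

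It is also fair to say that this is a minimal-risk pilot, and that with one clinic per arm even the interaction cannot isolate the pathway from other events particular to one clinic.

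**Conclusion.** The point holds as under-specification with a concrete better method available. The plan names its comparator but does not say how the between-clinic comparison combines with the pre/post data, and no stated contrast is, as written, net of both shared change and baseline clinic differences.

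The actual size and direction of bias cannot be known from the documents. The odds ratios of 1.00 to 2.15 (T0 windows) or 1.00 to 1.69 (V0 baseline), and the 75% rejection rate, are illustrations resting on the assumed 6.4% baseline, doubling and clinic difference. The omission does not depend on them. The stated 100% power is not an error for a simple two-group contrast; it is simply not the power of the interaction.

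This should be fixed but ranks no higher than that: it is a cheap improvement, whose downside is lower power for lab testing.

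**What to change.** - Make the primary analysis of the composite one GEE model with clinic, period and clinic-by-period terms, and name the interaction as the pathway effect. In the time series, add clinic-by-level and clinic-by-trend terms at T0 and T6m.
- Use the same index date and windows in both clinics.
- Fix the effect scale in advance. If baseline DPP referral is 0%, as the power section assumes, a log-odds interaction is not estimable, so use a risk difference there.
- Label uncontrolled pre/post changes as descriptive.
- Restate power for the interaction, giving the assumed control-clinic change, correlation and analysed sample size, and add the composite, for which none is given. With a flat control and ρ = 0, 80% power needs a rise from the assumed 6.4% to 10.6% at 1200 per clinic, or to 12.6% at 600.
- State as a limitation that one clinic per arm cannot exclude a clinic-specific shock.

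The cost is wording and model terms, with no new data. Lab testing is the planned effect that pays for it: below the quoted 100% even with a flat control clinic, and 41.4% to 69.3% at 1200 per clinic if the control clinic rises 5 points while the intervention clinic still reaches 60%.

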**Implementation and Evaluation of a Diabetes Prevention
Clinical Pathway in Primary Care**

NCT05265312

Date: 7/11/2023

Introduction

Abstract and Background:

Prediabetes is a significant public health problem affecting 88 million U.S. adults. Evidence suggests that the vast majority of people with prediabetes are unaware that they have this condition and many are not receiving appropriate care for prediabetes, including referral to evidence-based programs like the Diabetes Prevention Programs. In our retrospective cohort study of patients with prediabetes from Johns Hopkins Health Systems, we found that the rates of prediabetes clinical care activities are low. In our qualitative studies, we found that primary care physician (PCP) barriers include low knowledge about Diabetes Prevention Programs and misperceptions of insurance coverage of these programs and inadequate clinical staff to address prediabetes. Common patient barriers to taking action to prevent diabetes include lack of motivation, time and resources.

Primary Hypothesis: We hypothesize that the clinical pathway will result in increased clinician screening and intervention and improve patient engagement in diabetes prevention. We will compare results from the intervention clinic compared to a control clinic. If successful, we plan to implement and test the effectiveness of this clinical pathway across the entire health system.

Purpose of the Study Protocol: As described above, we have conducted several studies to understand current practices in prediabetes care across the Johns Hopkins Health Systems. In our retrospective cohort study of patients with prediabetes from Johns Hopkins, we found that the rates of prediabetes clinical care activities are low. Within 12 months, 63.4% had repeat glycemic testing, yet only 10.4% had coded diagnoses of prediabetes, 1.0% were referred for nutrition services, and 5.4% were prescribed metformin. We were unable to evaluate uptake of Diabetes Prevention Programs (DPPs) since a referral order was not in place until recently. In our qualitative studies, we found that clinician barriers include low knowledge about DPPs and misperceptions of insurance coverage of these programs and inadequate clinical staff to address prediabetes. Common patient barriers to taking action to prevent diabetes include lack of motivation, time and resources.

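### The pre/post logistic GEE may give no usable estimate for DPP enrolment, because pre-period events may be zero or very few and the plan names no alternative

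*Combined protocol and SAP*

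**What the plan says.** Statistical Methods lists a comparison of the primary and secondary outcomes between clinics, an interrupted time series over three periods, and a pre/post model: "We will compare these outcomes in the pre- and post-intervention periods using logistic regression models with generalized estimating equations". The outcomes meant are the primary and secondary ones. The first secondary outcome is whether patients "enroll in the DPP". Nothing is said about zero or sparse cells.

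Sample Size Determination and Power assumes a "change in rate of referral to DPPs from 0% to 25" per cent. The other three starting rates in that section are attributed to the institution's own data; this one is not. Purpose of the Study Protocol explains why no measured rate exists: "We were unable to evaluate uptake of Diabetes Prevention Programs (DPPs) since a referral order was not in place until recently". The plan gives no baseline rate for DPP enrolment.

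The pre-period is the 12 months before each patient's own V0 (Study Procedures). The primary outcome combines DPP referral, nutrition referral and metformin start. Control-clinic PCPs can also refer to a DPP.

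**The concern.** A logistic model compares log-odds. If no patient has the event before implementation, the pre-period log-odds are minus infinity and the period odds ratio has no finite value. If only a few patients do, the estimate is finite but its precision is set by those few events, whatever the size of the trial. The plan's own starting value for DPP referral is exactly where this happens, and enrolment that follows referral should be rarer still.

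At stake is the pre/post result for secondary outcome 1. A large rise could be reported with p near 1 or an interval too wide to interpret, or the method could be changed after the model is seen to fail.

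The recent arrival of the order also affects the composite primary outcome, though not its estimability. If the order was unavailable for part of the look-back, a within-clinic pre/post odds ratio mixes uptake of the pathway with the order becoming available.

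**Working it through.** **Inputs.** From the plan: 1200 patients per clinic, DPP referral 0% to 25%, nutrition referral 1.0%, metformin prescribed 5.4%. Assumed: alpha 0.05 (not stated in the plan) and a control-clinic implementation rate of 2% (24/1200). The intervention clinic's 25% (300/1200) is the planned referral rate, used for illustration because no enrolment rate is given.

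**1. The plan's power figure.** A two-proportion calculation with 1200 per group, 0 against 0.25, gives power 1.000, one- or two-sided. The stated 100% is reproduced. It concerns a difference in proportions, which is well defined at 0%; the log-odds used by the planned model are not.

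**2. Zero pre-period events.** The log-odds are ln(y/(n − y)), which is minus infinity at y = 0. Logistic GEE fits gave:
- Intervention clinic alone, 0/1200 then 300/1200: period coefficient 28.5, SE about 18,000, p = 0.999.
- Both clinics at 0/1200, then 300/1200 and 24/1200: clinic-by-period coefficient 2.78, SE about 21,000, p = 1.00.

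Both fits reported convergence. The same intervention-clinic counts give a risk difference of 0.25 with SE √(0.25 × 0.75/1200) = 0.0125.

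**3. Few pre-period events.** Each cell adds about 1/y + 1/(n − y) to the variance of a log-odds contrast.
- *Within the intervention clinic, one pre-period event.* Log-OR = ln(300/900) − ln(1/1199) = −1.10 + 7.09 = 5.99. SE = √(1/1 + 1/1199 + 1/300 + 1/900) = 1.00. The 95% interval for the odds ratio runs from about 56 to about 2,850.
- *Clinic-by-period term, one pre-period event per clinic.* Estimate 2.79, SE 1.43, p = 0.051. With six per clinic, the SE is 0.62.
- *Implementation period only, between clinics.* Log-OR = ln(300/900) − ln(24/1176) = 2.79. SE = √(1/300 + 1/900 + 1/24 + 1/1176) = 0.22.
- *The same contrast as a risk difference.* 0.25 − 0.02 = 0.23. SE = √(0.25 × 0.75/1200 + 0.02 × 0.98/1200) = 0.013. Subtracting one pre-period event per clinic leaves both figures essentially unchanged.

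**4. How likely is a zero?** For a true pre-period rate p, P(zero in one clinic) = (1 − p)^n, and P(zero in at least one clinic) = 1 − (1 − P(zero in one clinic))². A zero in either clinic is enough to make a clinic-by-period term infinite. Statistical Methods restricts analysis to patients seen in the first 6 months, so fewer than 1200 may qualify; 600 is shown as an assumption.

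| True rate | Expected events, n = 1200 | Zero in one clinic, n = 1200 | Zero in at least one, n = 1200 | Zero in at least one, n = 600 |
|---|---|---|---|---|
| 0.05% | 0.6 | 0.55 | 0.80 | 0.93 |
| 0.1% | 1.2 | 0.30 | 0.51 | 0.80 |
| 0.25% | 3 | 0.05 | 0.10 | 0.40 |
| 0.5% | 6 | 0.002 | 0.005 | 0.10 |

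**5. The composite.** Its pre-period rate without any DPP referral lies between 5.4% (full overlap of nutrition referral and metformin) and 6.4% (no overlap). Under independence it is 1 − 0.99 × 0.946 = 6.3%, or 76/1200. With assumed implementation counts of 357/1200 and 96/1200, the clinic-by-period term is 1.58 with SE 0.21. The model is estimable.

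**The case against.** The strongest reply is that Statistical Methods also specifies a between-clinic comparison, which covers DPP enrolment. That stands: the contrast is finite on the logit scale if the control clinic has at least one event, and control PCPs may refer to DPPs. A reader might infer that DPP enrolment cannot be analysed under this plan at all; the documents do not support that.

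Second, the 0% is a planning value for referral, not an observed rate and not an enrolment rate. Uptake is described as unmeasured, not as nil. The order was introduced recently, and the look-back rolls with each patient's V0, so a later V0 can place part of it after launch. A reader might infer that the pre-period count is zero by construction; that too is unsupported. The failure is a real risk, not a certainty. An exact zero needs a very low rate, although sparse counts also give poor precision.

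Third, a reader might infer that the primary analysis fails. It does not: two components have non-zero baseline rates, and DPP referral alone is not a listed outcome.

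Fourth, the plan does not write out a clinic-by-period term, so the figures for that term describe one natural reading. The within-clinic odds ratio, which the pre/post wording does cover, has the same defect at zero.

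Finally, an analyst would notice an SE in the thousands. Probably so, but the plan does not say what would then be done.

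**Conclusion.** The point holds, limited to DPP enrolment and to DPP referral if it is reported alone. If no pre-period event is observed, the pre/post logistic GEE has no finite period odds ratio. If there is one event per clinic, a clinic-by-period term has SE about 1.4 for an assumed 23-point effect that a risk difference estimates with SE about 0.013. The plan provides no alternative. These sizes rest on 1200 patients per clinic, an assumed 2% control rate and the planned 25% referral rate; true enrolment may be lower.

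The between-clinic comparison and the composite primary outcome remain estimable. For the composite, the caution concerns interpretation: its within-clinic pre/post odds ratio should not be read on its own as the effect of the pathway. The between-clinic comparison helps here, because both clinics have the same Epic tools, including the DPP referral order.

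**What to change.** Before analysis, amend Statistical Methods in three ways.

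1. For DPP enrolment, and DPP referral if reported alone, replace the pre/post logit contrast with the between-clinic risk difference in the implementation period, with robust SE, from an identity-link GEE or by marginal standardisation. If an odds ratio is wanted, name a penalised or exact method. Make this the rule whatever the pre-period count turns out to be, and report that count.
2. For the composite, base statements about the pathway on the comparison with the control clinic.
3. Add a sensitivity analysis of the composite without the DPP component, and state when the referral order became available relative to the look-back.

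The cost is SAP wording and one extra analysis, with no new data. The drawback is that this outcome's effect will be on a different scale from the others. With one clinic per arm, the robust SE reflects variation between patients only, so the change does not remove differences between the clinics themselves.
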